1.0 Study Summary

Study Title	Preoperative survey to evaluate patient allergy list, type of response to listed medication, and its relevance to perioperative care
Study Design	Anonymous, patient survey
Primary Objective	To determine allergies listed by patient and type of response which resulted in the allergy determination
Secondary Objective(s)	To determine the impact of the allergy list on anesthetic care
Study Population	Patients neonate to 21 years of age presenting for anesthetic care
Sample Size	1000
Study Duration	3 years

2.0 Methods

- 2.1 Although perioperative hypersensitivity reactions including anaphylaxis are rare, they may result in significant morbidity and mortality. The incidence of perioperative hypersensitivity reactions to medications, surgical equipment, and biological substances varies widely. Studies using large databases from France, Australia, and the United Kingdom (UK) have reported a significant variation in incidence ranging from 1:1361 to 1:20,000. Neuromuscular blocking agents (NMBAs), latex containing products, and antibiotics are identified as the agents most commonly responsible for perioperative hypersensitivity reactions. Newer NMBAs such as rocuronium may be associated with more frequent allergic reactions compared to older NMBAs, while the incidence of hypersensitivity to latex is decreasing as a result of its elimination from the perioperative environment and identification of at-risk patients.
- 2.2 Part of the routine preoperative evaluation is identification of previous allergies and avoidance of those medications during the perioperative period. For the purpose of our routine anesthetic care, we rely on the electronic medical record and the list of allergies provided. Although this is generally effective, it may be that allergies are erroneously listed and not based on good medical practice. For example, apnea following administration of an opioid such as fentanyl or diarrhea with the administration of Augmentin may be listed as allergies. The purpose of the current study is to evaluate allergies listed in the electronic medical record (EMR) of patients presenting for surgery and determine through a brief interview of the parent or guardian when that allergy was identified

NATIONWIDE CHILDREN'S HOSPITAL
SHORT PROTOCOL (Waiver of Consent or Verbal Consent)

PROTOCOL TITLE: Preoperative survey to evaluate patient allergy

and the exact symptomatology that resulted in determination of the allergy.

- 2.3 In addition to acute and chronic issues associated with substance abuse, these medications and substances can impact the perioperative care of patients and interact with anesthetic agents. Preoperative screening for these issues is now undertaken by an on-line preoperative questionnaire sent to the parents to complete prior to anesthetic care. Given the nature of such concerns and these issues, it is likely that there is under-reporting of these problems for various reasons.
- 2.4 Regardless of the history that is provided by the parents, no change in the allergy listing will be made and no specific change in the anesthetic plan mandate. The study will only involve identification of the listed allergies from the EMR and investigation into the symptoms that prompted this allergy listing. The purpose is to evaluate demographics and prevalence of allergies in patients presenting for surgery, evaluate the medical decision making process behind allergy identification, and determine its potential impact on perioperative care. For example, when patients are labelled as penicillin-allergic, it may be decided not to use cefazolin for prophylaxis of surgical site infections. Instead other antibiotics with a greater adverse effect profile such as vancomycin or clindamycin may be used.
- 2.5 The participants will be asked to complete a survey in REDCap using an iPad during the visit.
- 2.6 The information collected will include only demographic data including age, weight, gender, race and ethnicity. Survey data will be coded and will not include patient information. Completion of the survey will take approximately 10-15 minutes. Explanation of the study, its confidentiality, and the purpose will take approximately 5-10 minutes.
- 2.7 OU will be a relying site since one of their medical students will be collecting data for the study. All patients and data will come from NCH and all work on the study will be done at NCH.

3.0 Data Banking

- 3.1 All data collected during this study will be stored in a secure location, and only the collaborators directly involved with this research project will have access to this information. In addition, all electronic files will be stored on a secure, password-protected network. No data will be shared with OU.
- 3.2 Data will be stored for 6 years after the study is completed.
- 3.3 Data will not be stored for future use.

NATIONWIDE CHILDREN'S HOSPITAL
SHORT PROTOCOL (Waiver of Consent or Verbal Consent)

PROTOCOL TITLE: Preoperative survey to evaluate patient allergy

4.0 Inclusion and Exclusion Criteria

- 4.1 *Inclusion:* Patients 0-21 years of age presenting for surgery or procedure requiring anesthesia.
- 4.2 *Exclusion:* Patients who are not able cognitively to complete the computerized survey due to physical or intellectual impairment or communication issues related to non-English speaking patients.

5.0 Vulnerable Populations

- 5.1 This research involves children but does not involve greater than minimal risk under 21 CFR §50.51/45 CFR §46.404.
- 5.2 All data collected during this study will be stored in a secure location, and only the collaborators directly involved with this research project will have access to this information. In addition, all electronic files will be stored on a secure, password-protected network.
- 5.3 The subjects will not be exposed to greater than minimal risk.
- 5.4 Parents/legal guardians will be asked to give verbal consent and children will provide assent.

6.0 Number of Subjects (Records)

- 6.1 1000.

7.0 Recruitment Methods

- 7.1 Patients will be identified using the operating room schedule. The study coordinator, PI, or sub-investigators will screen and identify appropriate participants. Screening participants will occur according to the protocol defined inclusion and exclusion criteria under the auspices of a partial waiver in accordance with the HIPAA privacy rule.
- 7.2 Potential subjects will be approached in the pre-op area on the day of surgery by a member of the research team. The study will be explained to the patient and parents/guardians and they will be provided a copy of the consent form to review.

8.0 Withdrawal of Subjects

- 8.1 Patients may withdraw from the study at any time.
- 8.2 There are no anticipated circumstances under which subjects will be withdrawn from the research without their consent.

9.0 Data Management and Confidentiality

NATIONWIDE CHILDREN'S HOSPITAL
SHORT PROTOCOL (Waiver of Consent or Verbal Consent)

PROTOCOL TITLE: Preoperative survey to evaluate patient allergy

- 9.1 All data collected during this study will be stored in secure password protected computer files to which only trained members of the research team and collaborators directly involved with this research project will have access.
- 9.2 The data will be stored for the duration of the study and retained for 6 years after the study is completed per NCH as this meets both HIPAA and OHRP regulations.
- 9.3 No data will be transmitted to or from external institutions.
- 9.4 Subjects will be assigned a study identification number and no identifiers will be entered into REDCap. Names and MRNs will not be recorded.

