3.0 How long will identifying information on each participant be maintained?
Identifying information on each participant will be retained for 6 years after the research is complete which meets both HIPAA and OHRP regulations.

4.0 Describe any plans to code identifiable information collected about each participant. Subjects will be assigned a study identification number and no identifiers will be entered into REDCap. Names and MRNs will not be recorded.

5.0 Check each box that describes steps that will be taken to safeguard the confidentiality of information collected for this research:

- Research records will be stored in a locked cabinet in a secure location
- Research records will be stored in a password-protected computer file
- The list linking the assigned code number to the individual subject will be maintained separately from the other research data
- Only certified research personnel will be given access to identifiable subject information

6.0 Describe the provisions included in the protocol to protect the privacy interests of subjects, where "privacy interests" refer to the interest of individuals in being left alone, limiting access to them, and limiting access to their information. (This is not the same provision to maintain the confidentiality of data.) Subject information will not be given to any other investigators. Subjects and their information will be closely monitored and guarded by study staff; there will be limited access to patients and their information by trained study staff; and subject information will only be shared and discussed between study staff specific to this study

Confidential Health Information

1.0 Please mark all categories that reflect the nature of health information to be accessed and used as part of this research.

NATIONWIDE CHILDREN'S HOSPITAL
SHORT PROTOCOL (Waiver of Consent or Verbal Consent)

PROTOCOL TITLE: Preoperative survey to evaluate patient allergy

- Demographics (age, gender, educational level)
- Diagnosis
- Laboratory reports
- Radiology reports
- Discharge summaries
- Procedures/Treatments received
- Dates related to course of treatment (admission, surgery, discharge)
- Billing information
- Names of drugs and/or devices used as part of treatment
- Location of treatment
- Name of treatment provider
- Surgical reports
- Other information related to course of treatment
- None

2.0 Please discuss why it is necessary to access and review the health information noted in your response above.

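### The protocol conflicts on whether a link to the child is kept, and no rule limits enrolment to one survey per child, so repeat entries are possible and, if 9.4 governs, could not be removed later

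*Protocol*

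**What the plan says.** On identity, the protocol makes several statements:

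- Section 1.0 gives the design as "Anonymous, patient survey".
- Section 2.6 says "Survey data will be coded and will not include patient information".
- Section 9.4 says "Subjects will be assigned a study identification number and no identifiers will be entered into REDCap", followed by "Names and MRNs will not be recorded". Section 15.0, item 4.0 repeats both statements.
- Section 15.0, item 3.0 says "Identifying information on each participant will be retained for 6 years after the research is complete".
- Section 15.0, item 5.0 is a checklist of safeguards. One option reads "The list linking the assigned code number to the individual subject will be maintained separately from the other research data". The text available does not show whether that box, or any box for recorded identifiers in item 1.0, was ticked.

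On who may enter, Section 4.1 admits "Patients 0-21 years of age presenting for surgery or procedure requiring anesthesia". Section 4.2 excludes only for cognitive, physical or language reasons. Section 1.0 gives "Study Duration 3 years", without a separate accrual period. Section 7.1 has staff screen the operating room schedule against these criteria.

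On the count and the analysis, Section 6.0 gives 1000 under a heading that names both subjects and records. Section 2.4 lists the prevalence of allergies in patients presenting for surgery among the aims. The SAP plans medians, interquartile ranges, frequencies and percentages, and has no rule for repeat records.

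**The concern.** There are two separate problems.

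First, the identity statements cannot all hold. A survey that is anonymous and records no names or MRNs leaves no obvious identifying information to keep for six years. If such information is kept, the survey is coded rather than anonymous. Study staff cannot tell from the protocol whether a link should exist.

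Second, eligibility attaches to the presentation, not to the child. A child who returns for another anesthetic meets 4.1 again, and nothing in 4.2 excludes that child. This is true whether or not a link is kept. The link decides only whether a repeat could be found afterwards: under 9.4 as written it could not.

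What is at stake is the denominator. With repeats, 1000 records are fewer than 1000 children, and each percentage is per record. Children with many anesthetics have the most chances to be entered again. If they also carry more allergy labels, the repeats push prevalence upward relative to the children actually enrolled.

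**Working it through.** **The plan's own figure.** The 1000 comes with no precision target, expected rate or power, so it can be neither reproduced nor refuted. For scale, the 95% half-width at n = 1000 is 1.96 × √(p(1−p)/1000): 1.86 points at p = 0.10 and 3.10 points at p = 0.50.

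**Inputs.** From the documents: 1000 records, 3 years, eligibility at each presentation, no exclusion for earlier participation. Not in the documents, so assumed throughout: visits per child (k), the chance that a visit is captured (f, the same at first and later visits), the share of children with many visits (s), and label prevalence in each group. The 1.7% capture value implies 1000/0.017, about 59,000 eligible visits, a volume that the documents do not state.

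**Step 1: chance of a second entry.** Among children enrolled at least once, the share entered twice or more is

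[1 − (1−f)^k − k f (1−f)^(k−1)] / [1 − (1−f)^k].

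| f | k | share entered twice or more |
|---|---|---|
| 0.017 | 2 | 0.9% |
| 0.017 | 4 | 2.6% |
| 0.017 | 10 | 7.5% |
| 0.05 | 10 | 21.5% |

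**Step 2: effect on prevalence.** Let a share s of children have 10 visits and label prevalence 40%, and the rest 1 visit and 10%. Per child in the population, expected records are 10sf + (1−s)f and expected unique enrolled children are s[1 − (1−f)^10] + (1−s)f.

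- *Low scenario, s = 0.02, f = 0.017.* Records 0.0034 + 0.01666 = 0.02006; unique 0.00315 + 0.01666 = 0.01981. Repeats are 1 − 0.01981/0.02006, about 12 per 1000 records. Prevalence is 15.1% per record and 14.8% per enrolled child, a difference of 0.3 points.
- *High scenario, s = 0.05, f = 0.10.* Records 0.0500 + 0.0950 = 0.1450; unique 0.0326 + 0.0950 = 0.1276. Repeats are about 120 per 1000 records. Prevalence is 20.34% per record and 17.66% per enrolled child, a difference of 2.7 points.

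In general the shift is d × (q − p), where d is the share of records that are repeats, q is prevalence in the children repeated and p is prevalence in unique enrolled children. Check: 0.0124 × (0.40 − 0.148) = 0.003 and 0.120 × (0.40 − 0.177) = 0.027. If q = p, there is no shift.

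**Step 3: precision.** If 100 of 1000 records are second records with identical answers, the design effect is (4 × 100 + 800)/1000 = 1.2 and the effective n is 1000/1.2 = 833. The half-width at p = 0.50 rises from 3.10 to 3.39 points, a small loss.

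**Step 4: what one survey per child does not cure.** Under the same inputs, prevalence over all children is 0.02 × 40% + 0.98 × 10% = 10.6% (low) and 0.05 × 40% + 0.95 × 10% = 11.5% (high). The de-duplicated figures are 14.8% and 17.7%. Removing repeats closes 0.3 of a 4.5-point gap, or 2.7 of 8.8. The remainder arises because frequent attenders are more likely to be sampled at all.

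**The case against.** The strongest reply is that a link may well exist. The protocol calls the data coded, assigns study numbers, speaks of retained identifying information and offers a separate linking list as a safeguard. A reader might infer from 9.4 that no link exists and that repeats must go undetected. The documents do not support this, because it takes one side of an unresolved conflict and the relevant tick marks are not visible. For the same reason it cannot be asserted that an EMR entry can never be rechecked, or that a withdrawn record can never be traced; Section 8.1 allows withdrawal but does not mention deleting submitted data. This part of the reply stands, so those consequences are conditional on 9.4.

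Second, staff work from the schedule, have chart access (10.2) and approach each family in person (7.2). A family may say that it has already taken part, or decline a second unpaid survey. That is fair, and it means that equal capture at first and later visits leans towards too many repeats. No such check is written, however, and the criteria as they stand admit a returning child.

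Third, the upward bias is not a fact. A reader might infer that the reported prevalence will be too high, but if the aim in 2.4 is prevalence over presentations, per-record percentages are the right quantity. The bias needs a per-child target and more labels among returning children, neither of which the documents settle.

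Fourth, a reader might infer that confidence intervals will be too narrow. The SAP plans none, and Step 3 shows that the precision loss would be small.

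**Conclusion.** The point holds in a limited form. Two things rest on the text alone: the statements on anonymity, names and MRNs, and six-year retention need reconciling; and the criteria allow the same child to be entered more than once, with no rule for repeats in either document. If 9.4 governs, analysts could not repair this after collection, which makes it more than a missing detail.

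The size cannot be derived from the documents. Under the assumed scenarios, 12 to 120 of 1000 records are repeats and prevalence per record exceeds prevalence per enrolled child by about 0.3 to 2.7 points. The low end is negligible beside a half-width of 1.86 points at 10% prevalence. The high end slightly exceeds the half-width at its own de-duplicated prevalence, 1.96 × √(0.177 × 0.823/1000) = 2.4 points, but it needs 10% capture, 5% of children with ten visits and a fourfold prevalence ratio all at once. The case for acting rests on how little prevention costs, not on a demonstrated large bias.

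**What to change.** 1. Add to Section 4.2 an exclusion for children already enrolled in this study. At approach, or as the first REDCap item, ask whether the survey has already been completed for this child, and stop if so. State in Sections 1.0 and 6.0 that 1000 means unique children. This works with or without a link and preserves anonymity. It costs one criterion, one question and a wording change; it relies on family recall, so a few repeats may still pass.

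2. Reconcile the identity statements in one of two ways. Either state that no link is kept and delete the six-year identifier sentence in Section 15.0, item 3.0; or call the survey coded, correct 9.4 and item 4.0, and describe the link, where it is held and when it is destroyed. The second option also allows a check before each enrolment and an analysis of the first survey per child, at the price of strict anonymity. Each is an IRB wording amendment; the second also needs a small log.

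3. Add a sentence to the SAP that the unit of analysis is the enrolled child and that results describe enrolled children presenting for anesthesia, not all children. This costs nothing and covers the over-representation of frequent attenders that one survey per child leaves in place.

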10.0 Provisions to Protect the Privacy Interests of Subjects

- 10.1 Subject information will not be given to any other investigators. Subjects and their information will be closely monitored and guarded by study staff; there will be limited access to patients and their information by trained study staff; and subject information will only be shared and discussed between study staff specific to this study.
- 10.2 Only the absolute minimum information necessary for this study will be collected from the patient's records. Access to the patients' charts will be limited to only the research team who have completed all the necessary training.
- 10.3 We will only be publishing de-identified research information.

11.0 Economic Burden to Subjects

- 11.1 There will be no costs to subjects and subjects will not receive any compensation.

12.0 Consent Process

- 12.1 The consent process will begin in the preoperative surgery unit on the day of surgery, by PI, Sub-Investigators, Study Coordinators, and/or trained research staff.
- 12.2 The study will be thoroughly explained to the patient and their family. There will be ample time allotted for questions and answers. An explanation of voluntary participation will take place, and the family will be asked if they are interested in participating in the study. The patient will then be enrolled in the study with the understanding that they can elect to stop the study and be withdrawn from the study at any time.
- 12.3 Potential subjects will be provided a written information sheet and verbal consent will be obtained.

NATIONWIDE CHILDREN'S HOSPITAL
SHORT PROTOCOL (Waiver of Consent or Verbal Consent)

PROTOCOL TITLE: Preoperative survey to evaluate patient allergy

13.0 Setting

13.1 Potential subjects will be identified from the surgery schedule in Epic and recruited from the pre-op area of the surgery unit. Surveys will be completed via REDCap on iPads in the pre-op area.

14.0 Resources Available

14.1 The research team is comprised of 2 PhD research scientists, a research nurse, a research coordinator, two research associates, and two research interns. All team members will meet with the PI, co-investigators, and the research team for a study start up meeting for training about the protocol, research procedures, and their duties and functions.

15.0 Protected Health Information Recording

1.0 Indicate which subject identifiers will be recorded for this research.

- Name
- Complete Address
- Telephone or Fax Number
- Social Security Number (do not check if only used for ClinCard)
- Dates (treatment dates, birth date, date of death)
- Email address , IP address or url
- Medical Record Number or other account number
- Health Plan Beneficiary Identification Number
- Full face photographic images and/or any comparable images (x-rays)
- Account Numbers
- Certificate/License Numbers
- Vehicle Identifiers and Serial Numbers (e.g. VINs, License Plate Numbers)
- Device Identifiers and Serial Numbers
- Biometric identifiers, including finger and voice prints
- Other number, characteristic or code that could be used to identify an individual
- None (Complete De-identification Certification Form)

2.0 Check the appropriate category and attach the required form* on the Local Site Documents, #3. Other Documents, page of the application. (Choose one.)

- Patient Authorization will be obtained. (Include the appropriate HIPAA language (see Section 14 of consent template) in the consent form OR attach the [HRP-900, HIPAA AUTHORIZATION](#) form.)
- Protocol meets the criteria for waiver of authorization. (Attach the [HRP-901, WAIVER OF HIPAA AUTHORIZATION REQUEST](#) form.)
- Protocol is using de-identified information. (Attach the [HRP-902, DE-IDENTIFICATION CERTIFICATION](#) form.) (Checked "None" in 1.0 above)

NATIONWIDE CHILDREN'S HOSPITAL
SHORT PROTOCOL (Waiver of Consent or Verbal Consent)

PROTOCOL TITLE: Preoperative survey to evaluate patient allergy

- Protocol involves research on decedents. (Attach the [HRP-903, RESEARCH ON DECEDENTS REQUEST](#) form.)
- Protocol is using a limited data set and data use agreement. (Contact the Office of Technology Commercialization to initiate a Limited Data Use Agreement.)

*Find the HIPAA forms in the [IRB Website Library, Templates](#).

Attach the appropriate HIPAA form on the “Local Site Documents, #3. Other Documents”, page of the application.

